10.4 Planned analyses

The main statistical analysis is planned when all patients have completed the six months visit. Deviation from the original statistical plan will be described and justified in the Clinical Study Report. Amendments to plan can be done until day of database lock.

10.5 Statistical Analysis **[name]?

Results will be reported as mean scores with standard deviation or proportions as appropriate.

To compare the two groups on the primary outcome, we will use a general linear model with treatment group was factor and adjust for duration of symptoms, gender and age. The analysis will be conducted according to the intention to treat principle.

For other analysis, comparison between groups will be done with e.g. independent samples t-test, nonparametric Mann-Whitney-U test or Pearsons chi-square test for crosstabs as appropriate.

P-values <0.05 are considered statistically significant.

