Centers:	Sørlandet Hospital + 5-10 other Norwegian hospitals
Study Period:	Estimated date of first patient enrolled: 01.10.15 Anticipated recruitment period: 01.10.15- 31.12.19 Estimated date of last patient completed: 31.12.20
Treatment Duration:	Six weeks
Follow-up:	13 months
Objectives	
Primary objective
 
To answer the question “is two weeks doxycycline treatment (currently suggested treatment) at least as effective as six weeks doxycycline treatment in Lyme Neuroborreliosis?”
 
Key secondary objectives
 
To provide a better understanding of the pathogenesis and long-term complaints, and to search for new biomarkers in LNB
 
To collect clinical data, blood, and CSF in a biobank for future research

Endpoints:	
Primary endpoint:
 
Improvement in composite clinical score defined as clinical score at inclusion minus clinical score at 6 months.
 
Secondary endpoints:
 
Fatigue Severity Scale (FSS) Patient Health Questionnaire (PHQ-15) Short Form 36 (SF-36) Blood and CSF findings MRI, and neuropsychological assessments in a subset of patients Adverse events

Study Design:	Multicenter, non-inferiority, randomized, penta-blind, placebo-controlled trial
Main Inclusion Criteria:	
1. Neurological symptoms suggestive of LNB without other obvious reasons and one or both of
a. Cerebrospinal fluid pleocytosis (≥ 5 leukocytes/mm³)b. Intrathecal Bb antibody production2. Signed informed consent
Main Exclusion Criteria	
- Age less than 18 years- Pregnancy, breast-feeding- Adverse reaction to tetracyclines- Treatment with cephalosporin, penicillin, or tetracycline the last 14 days- Serious liver or kidney disease that contraindicates use of doxycycline- Lactose intolerance- Need to use medications contraindicated according to SmPC of the IMP
Sample Size:	120 patients
Efficacy Assessments:	Comparison of clinical outcome six months after end of treatment between the two treatment groups.
Safety Assessments:	Subjective experiences and blood tests including hematology and biochemistry for four weeks after ended treatment.

TABLE OF CONTENTS

CONTACT DETAILS.....	2
SIGNATURE PAGE	3
PROTOCOL SYNOPSIS.....	4
TABLE OF CONTENTS	5
LIST OF ABBREVIATIONS AND DEFINITIONS OF TERMS.....	8
1 INTRODUCTION.....	9
1.1 Background – Lyme Neuroborreliosis (LNB).....	9
1.2 Background - Therapeutic Information.....	9

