2.1 Primary Endpoint

The primary endpoint is improvement on a composite clinical score (Table 2) from inclusion to six months after ended treatment defined as clinical score at inclusion minus clinical score at six months.

Subjective symptoms	
Subjective symptoms related* by the patient to the current/recent LNB	Score
Malaise (sykdomsfølelse, redusert almentilstand)	
Fatigue (trøtthet, utmattelse)	
Headache (hodepine)	
Neck and/or back pain (nakke og/eller ryggsmerte)	
Abdominal and/or breast pain (smerter i bryst og/eller mageregion)	
Arm pain (smerter i armer)	
Leg pain (smerter i ben)	
Generalized pain located to joints and/or muscles (smerter i "hele kroppen" (ledd og muskler))	
Memory and/or concentration problems (hukommelse og/eller koncentrasjonsproblemer)	
Other (annet)	
Objective findings, PNS	
Findings related* to the current/recent LNB	Score
Facial palsy (facialisparese)	
Paresis of eye muscles (øyemuskelparese)	
Reduced hearing (redusert hørsel)	
Other cranial neuropathies (andre hjernenerveutfall)	
Cervical radicular sensory findings ^a (cervikale radikulære sensoriske funn)	
Cervical radicular paresis ^b (cervikal radikulær parese)	
Thoracal radicular sensory findings ^a (thoracale radikulære sensoriske funn)	
Lumbar radicular sensory findings ^a (lumbale radikulære sensoriske funn)	
Lumbar radicular paresis ^b (lumbal radikulær parese)	
Non-radicular sensory findings ^c (ikke-radikulære sensoriske funn)	
Non-radicular paresis ^d (ikke-radikulær nevropati med pareser)	
Other (annet)	
Objective findings, CNS	
Findings related* to the current/recent LNB	Score
Central findings ^e in one extremity (sentralnervøse funn i en ekstremitet)	
Central findings ^e in a hemi pattern (sentralnervøse funn i en kroppshalvdel)	
Central findings ^e in both legs (sentralnervøse funn i begge ben)	
Central findings ^e in all extremities (sentralnervøse funn i alle ekstremiteter)	
Gait ataxia (gangataksi, ustøhet)	
Dysphasi/aphasi (talevansker)	
Nystagmus (nystagmus)	
Involuntary movements including tremor (ufrivillige bevegelser inkl. skjelving)	
Cognitive impairment (kognitiv svikt/forvirring)	
Other (annet)	
Total score	

Table 2. Composite clinical score.

Each item is scored 0=none, 1=mild, without influence on daily life, or 2=severe, with influence on daily life.

Maximum total score=64 (sum of subjective symptoms and objective findings)

* Temporally and otherwise related to current LNB

^a Abnormal sensory findings in a radicular pattern

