4.2 Number of Patients

We plan to enroll 120 patients, 60 in each treatment arm.

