7 ASSESSMENTS

7.1 Assessment of Efficacy

The treatment efficacy will be assessed by measuring symptoms and signs six months after ended treatment and summarized on a composite clinical score which reports subjective symptoms and objective findings in a clinical neurological examination. The primary endpoint is improvement in the composite clinical score. The score is a modified version of a score used in an earlier treatment trial in LNB (5). Even if the score is not validated it is, in our opinion, the best way to assess outcome after LNB as it addresses and grades the most commonly reported remaining symptoms and signs. Our experience with the previous score was that it worked well, but some points were not entirely clear or somewhat overlapping. We therefore find it appropriate and more accurate to simplify it to reduce interrater disagreement and scale biases.

To support treatment effect assessment we have chosen several secondary endpoints; inflammatory findings in CSF as measured by cellcount, protein level and oligoclonal bands, fatigue as measured by FSS, burden of somatic symptoms as measured by PHQ-15, and health related quality of life as measured by SF-36. We will also apply proportion of patients with full recovery (score zero on the composite clinical score) as a secondary endpoint. In a subset of patients, MRI findings and neuropsychological profile will be a secondary endpoint.

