10.2 Randomization

10.2.1 Allocation- sequence generation

Computerized allocation to two or six weeks doxycycline (1:1) will be performed at Department of clinical research support, OUS by an internet based solution. Automatic e-mails with the result of the randomization will be sent to the involved hospitals.

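### The primary model has no hospital term and no stratification by hospital is described; adding both would be a cheap, minor gain in precision, not the repair of a bias.

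*Combined protocol and SAP*

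**What the plan says.** The synopsis gives the centres as "Sørlandet Hospital + 5-10 other Norwegian hospitals", which makes 6 to 11 hospitals; Section 4.1 speaks of 5–10 selected hospitals. Section 4.2 states: "We plan to enroll 120 patients, 60 in each treatment arm".

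On allocation, Section 10.2.1 states: "Computerized allocation to two or six weeks doxycycline (1:1) will be performed at Department of clinical research support, OUS by an internet based solution". It names no stratification factor and no block scheme.

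On analysis, Section 10.5 states: "we will use a general linear model with treatment group was factor and adjust for duration of symptoms, gender and age". No other section uses hospital in the allocation or the analysis.

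The primary endpoint in Section 2.1 is a change score, "defined as clinical score at inclusion minus clinical score at six months". Of the instrument, Section 7.1 says: "Even if the score is not validated it is, in our opinion, the best way to assess outcome after LNB". The same section explains that some points of the score used in a former trial were unclear or overlapping, so the sponsor chose to "simplify it to reduce interrater disagreement and scale biases". Section 4.1 provides for a trained contact person at each site, and Section 10.2.2 for blinded endpoint staff. No central rater and no check of agreement between raters is described.

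**The concern.** The score has 32 items, each graded 0 to 2, and each needs a judgement on severity and on relation to the disease. If improvement differs between hospitals, because recovery differs or because rating habits shift between inclusion and six months, a model without hospital counts that difference as noise. In a non-inferiority trial the conclusion rests on the width of a confidence interval, so avoidable noise costs power directly. Without stratification, chance can also place a hospital's patients mostly in one arm. If, on the other hand, the system does stratify by hospital and the document merely omits this, the stated model does not match the design and its standard error is too large.

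**Working it through.** **Inputs.** 120 patients, 60 per arm (Section 4.2). SD 2.6 (Section 10.1); this is the SD of the 12-month score in a former trial, not of change in this one. 6–11 hospitals (synopsis). The ICC, meaning the share of variance in improvement that lies between hospitals, is not given; I take 0 to 0.20. No dropout is assumed.

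**The planned size.** The figure of 120 cannot be reproduced, because no margin and no power are stated. As a reference case I solve for the margin that 60 per arm would support at one-sided 0.025 and 80% power:

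- SE = 2.6 × √(2/60) = 0.475
- margin = 2.6 × (1.960 + 0.842) × √(2/60) = 1.33

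This margin is my assumption and serves only to put the effect on a power scale.

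**Upper bound: hospital in the model and arms balanced within hospitals.** The residual SD becomes 2.6 × √(1 − ICC), power is Φ(1.33/SE − 1.96), and the patient equivalent is 120/(1 − ICC) − 120.

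| ICC | SE | Power | Patient equivalent |
|---|---|---|---|
| 0 | 0.475 | 80.0% | 0 |
| 0.05 | 0.463 | 82.0% | 6.3 |
| 0.10 | 0.450 | 84.0% | 13.3 |
| 0.20 | 0.425 | 87.9% | 30.0 |

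**Random intercept alone, allocation not stratified.** This was simulated with REML, 60/60 overall, for 6 equal, 11 equal and 11 unequal hospitals. Power changes by about 0, 1, 2 and 5–6 points at ICC 0, 0.05, 0.10 and 0.20. The reduction in SE is worth roughly 1 patient at ICC 0.05 and 4–6 patients at ICC 0.10, well short of the bound above.

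**Fixed hospital effects, allocation not stratified.** With 11 equal hospitals, power with the term against without it is 75% v 79% at ICC 0, 78% v 80% at 0.05, 80% v 81% at 0.10 and 84% v 81% at 0.20. Fixed effects can therefore lose power in small hospitals. The random intercept shows no such cost at ICC 0.

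**Validity of the stated model.** Without a hospital term and without stratification, the simulated two-sided type I error is 4.8–5.3%, which is nominal. With allocation stratified by hospital but hospital left out of the model, it is 4.7%, 4.0% and 3.3% at ICC 0.05, 0.10 and 0.20, which is conservative.

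**Imbalance within hospitals.** With 60/60 overall and no stratification, the chance that at least one hospital is split 2:1 or worse is about 38% with 6 hospitals of 20, 92% with 11 of about 11, and 99% with 11 unequal hospitals of 4–30 patients. The standard error already allows for this chance imbalance. It explains why the random intercept alone falls short of the upper bound.

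**The case against.** The strongest reply is that nothing invalid has been shown. Patients are randomised individually, so omitting hospital leaves the estimate unbiased and the type I error nominal. No ICC is documented, and zero is as compatible with the text as 0.10. The endpoint is a change score, so a hospital that always rates strictly cancels itself out if its habits are stable between visits. Sites are trained and endpoint staff are blinded. The missing margin and power are a far larger gap. All of this stands, and it makes the point minor. It does not remove it: differences in recovery, or rating that shifts between visits, do not cancel, the protocol does not require the same rater at both visits, and the random intercept costs essentially nothing if hospitals do not differ.

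A reader might infer more than the documents support:

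- **That the protocol calls its own score prone to disagreement between raters.** Section 7.1 describes weaknesses of the previous score and a simplification meant to reduce them. Only the lack of validation is stated of the current one.
- **That hospitals differ in case mix.** This is plausible, but no section says so; Section 3 documents only a staggered start.
- **That allocation is a simple coin toss.** Section 10.2.1 is silent on restriction, and Section 4.2 plans equal arms. Unequal totals would matter little in any case: a 65/55 split keeps 4 × 65 × 55 / 120² = 99.3% of the efficiency.

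**Conclusion.** The point holds as a minor efficiency improvement. The primary model omits hospital, and the allocation text leaves stratification by hospital open. The cost is some precision if hospitals differ in improvement, or a conservative test if allocation is in fact stratified. With SD 2.6 and an assumed margin of 1.33, the model change alone is worth about 1 power point at ICC 0.05, 2 at 0.10 and 5–6 at 0.20, and nothing at 0. The 6–13 patient equivalents at ICC 0.05–0.10 are a ceiling that needs balance within hospitals. The ICC and the margin are assumptions, and the SD is borrowed from a score level on a slightly different scale, so these figures show relative size and not the trial's actual power. The documents do not support a claim that the treatment estimate is biased or that false non-inferiority becomes more likely.

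**What to change.** - **Section 10.5:** add hospital as a random intercept to the primary model, fixed in writing before any unblinding. Section 10.4 allows changes to the plan until database lock. Small hospitals need no pooling, because the random intercept already gives them little weight. Fixed hospital effects are not advised unless allocation is stratified.
- **Section 10.2.1:** state whether the web system stratifies by hospital. If it does not, stratify patients still to be enrolled, with concealed block sizes that vary.

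The cost is a wording change and a change to the setup of the existing randomisation system. The downside is one more variance parameter to estimate and some incomplete blocks in small hospitals.

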2.2 Secondary Endpoints

Improvement of composite clinical score from inclusion to 12 months after end of treatment defined as clinical score at inclusion minus clinical score at 12 months. (Table1)

Fatigue Severity Scale (FSS) at six and 12 months after end of treatment. FSS is translated and validated for Norwegian purposes (12). It measures level of agreement (1– 7) with nine statements. The final score represents the mean value of the nine items. Severe fatigue is defined as a score >5 in a Norwegian population. Reported mean score in 20 American

healthy adults is 2.3 (13), and reported mean score in 50 Norwegian patients treated for LNB is 3.5 versus 2.1 in the control group (3).

Patient Health Questionnaire (PHQ-15) at six months. PHQ-15 is a brief, validated questionnaire, which consists of 13 questions concerning severity of different subjective somatic symptoms the last 4 weeks, and 2 questions concerning sleep and tiredness. Each item is scored from 0 to 2, and sum score ranges from 0 to 30. Sum scores of 5, 10, and 15 represent cutpoints for low, medium, and high symptom severity, respectively (27).

Short Form-36 (SF-36): SF-36 is a valid and reliable questionnaire assessing health related quality of life. It consists of 36 questions concerning general health perceptions, physical functioning, physical role functioning, emotional role functioning, social role functioning, bodily pain, vitality and mental health. A Norwegian normal material exist (28).

CSF findings at six and 12 months: Cell count, IgG index, OCB's, and *Bb* antibodies

Other laboratory tests, MRI, and neuropsychological assessments: In a subset of patients at inclusion and six months after end of treatment (WP4 of BorrSci).

Safety as measured by serious adverse events and less serious side effects of treatment (Table 3)

Table 3. Safety measures

Treatmentweek	0	1	2	3	4	5	6	7-10
Nausea		x	x	x	x	x	x	x
Vomiting		x	x	x	x	x	x	x
Diarrhea		x	x	x	x	x	x	x
Skin reactions		x	x	x	x	x	x	x
Vaginitis		x	x	x	x	x	x	x
Blodtests (Hb, Hb, white blood cell count with differential, platelet count, ASAT, ALAT, GT, ALP, Creatinine)	x		x		x			
Other AE or complications		x	x	x	x	x	x	x

Secondary and exploratory objectives and their endpoints and assessments are detailed in WP 3 and 4 (Appendix A)

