10 STATISTICAL METHODS AND DATA ANALYSIS

10.1 Determination of Sample Size ** [name]?

In a previous trial on well-characterized LNB patients, 102 patients were treated with either oral doxycycline or IV cephtriazone for two weeks. From this trial we have available outcome scores at 12 months from 93 patients, measured on a slightly different composite clinical scale, but with the same max score of 64. We consider the scales as so similar that the results from the former trial can be used in power analyses in the current planned trial. The mean score in the former trial was 1.7 with a standard deviation (SD) of 2.6.

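### Fatigue (FSS) is recorded at inclusion, but section 10.5 names only unadjusted tests for it; adjusting for the inclusion value would gain precision at little cost

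*Combined protocol and SAP*

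**What the plan says.** Section 2.2 lists "Fatigue Severity Scale (FSS) at six and 12 months after end of treatment" among the secondary endpoints. It is given as a score at each visit, whereas the composite clinical score is defined as inclusion value minus follow-up value. Section 7.1 includes "fatigue as measured by FSS" among the endpoints chosen to back up the assessment of treatment effect.

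The flow chart in section 6.1 marks FSS at baseline, end of week 10, six months and 12 months. The visit lists in 6.2.1, 6.2.3, 6.2.5 and 6.2.6 agree. PHQ-15 and SF-36 have no baseline entry.

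Section 10.5 specifies a general linear model for the primary outcome, with "treatment group was factor and adjust for duration of symptoms, gender and age". For everything else it says "For other analysis, comparison between groups will be done with e.g. independent samples t-test, nonparametric Mann-Whitney-U test", adds a chi-square test as a third example, and leaves the choice to what suits the data. It also promises means with standard deviations, or proportions. It does not mention confidence intervals.

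**The concern.** Section 1.1 names fatigue first among the common remaining complaints, and FSS is the only one of the three patient questionnaires with an inclusion value. The composite score uses its inclusion value by construction, because the endpoint is a difference from inclusion. For FSS the inclusion value has no stated role.

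At stake is the width of the interval on a supporting endpoint. In a trial asking whether the shorter course is at least as effective, a supporting scale is informative through the estimated difference and its interval. A non-significant P value from a two-sample test does not show similarity. If inclusion FSS predicts follow-up FSS, ignoring it makes that interval wider than it needs to be.

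**Working it through.** **Inputs from the documents.** Section 4.2: "We plan to enroll 120 patients, 60 in each treatment arm". Section 10.5: "P-values <0.05 are considered statistically significant"; sidedness is not stated, so two-sided is taken for FSS. Section 2.2 gives FSS means of 3.5 in treated patients and 2.1 in controls, but no SD and no correlation between inclusion and follow-up.

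**Inputs assumed.** Correlation ρ between inclusion and follow-up FSS of 0.2 to 0.6; FSS SD of 1.5 points; no dropout.

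**The plan's own figure.** No power or sample size is stated for FSS, so there is nothing to reproduce. Section 10.1 concerns the composite score: "The mean score in the former trial was 1.7 with a standard deviation (SD) of 2.6". That SD cannot be carried over to FSS.

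**Step 1, unadjusted comparison.** The 95% CI half-width is 1.96 × SD × √(2/n) = 1.96 × 1.5 × √(2/60) = 0.54 points. The difference detectable with 80% power is (1.96 + 0.84) × √(2/60) = 0.511 SD.

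**Step 2, adjusted for inclusion FSS.** The variance of the treatment difference is multiplied by 1 − ρ². The half-width and the detectable difference are multiplied by √(1 − ρ²). The equivalent unadjusted sample is 60/(1 − ρ²) per arm.

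| ρ (assumed) | Variance cut, ρ² | Half-width, points | Detectable difference, SD | Equivalent n per arm |
|---|---|---|---|---|
| 0 (unadjusted) | 0% | 0.54 | 0.511 | 60 |
| 0.2 | 4% | 0.53 | 0.501 | 62.5 |
| 0.3 | 9% | 0.51 | 0.488 | 65.9 |
| 0.5 | 25% | 0.46 | 0.443 | 80 |
| 0.6 | 36% | 0.43 | 0.409 | 93.8 |

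**Step 3, price of the covariates.** The table is a large-sample result. Estimating k covariates in N patients inflates the variance on average by a factor of about 1 + k/(N − k − 3). With four covariates and N = 120 this is 1 + 4/113 = 1.035. If duration, gender and age explain nothing about FSS, the net variance ratio is 0.96 × 1.035 = 0.99 at ρ = 0.2 and 0.64 × 1.035 = 0.66 at ρ = 0.6. If inclusion FSS also explains nothing, the loss is about 3.5% of variance.

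**Step 4, why not a change score.** With equal SDs at both visits, the variance of a change score relative to the follow-up score is 2(1 − ρ): 1.6 at ρ = 0.2, 1.0 at 0.5 and 0.8 at 0.6. Subtracting inclusion FSS would therefore lose precision for any ρ below 0.5. Adjustment in the model does not carry that risk.

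**The case against.** The strongest reply is that nothing here is an error. The list in section 10.5 is open, the tests are examples, section 10.2.2 fixes tables and figures before data are available, and section 10.4 allows the plan to be amended until database lock. A reader might infer that the plan rules out adjustment or discards inclusion FSS. The documents show only that no analysis using it is named. That part of the reply stands. But open wording does not supply a model, and if tables are to be fixed in advance, the FSS estimate has to be chosen in advance too.

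A reader might also infer that a chance imbalance in entry fatigue passes in full into the result. It does not. It carries over in proportion to the slope of follow-up on inclusion FSS: with equal SDs and ρ = 0.3, about 30% of it. Under 1:1 randomization the unadjusted comparison is unbiased, and its standard error already allows for chance imbalance.

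Nor does the Mann-Whitney option leave the reader without a difference in points. Section 10.5 promises arm means with SDs, from which a difference and an interval can be derived. What is missing is an explicit promise of the interval.

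Finally, the gain may be small. Inclusion FSS is taken in active disease and follow-up is at least six months after treatment, so a low correlation is plausible. This stands, and is why the range starts at 0.2.

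**Conclusion.** The point holds as a loss of efficiency. FSS has an inclusion value, the only methods named for it are unadjusted, and a better one is available from data the trial already collects. The validity of the FSS comparison and the primary analysis are not in question.

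The size rests wholly on assumption. The expected benefit runs from practically nothing at the low end of the range to about a third of the variance at the high end. Dropout would widen every half-width but leave the 1 − ρ² ratio unchanged. FSS carries no margin, power or decision rule, so this is a worthwhile improvement to a supporting analysis and does not change how the trial reaches its conclusion.

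**What to change.** In section 10.5, specify before database lock that FSS at six months and at 12 months is each compared with the primary outcome's general linear model (treatment, duration of symptoms, gender, age) plus inclusion FSS. Report the adjusted difference in FSS points with its 95% CI. Keep the Mann-Whitney test as a sensitivity analysis, since a 1–7 score may be skewed after recovery. State how a missing inclusion FSS will be handled.

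The cost is plan wording. No new data, visits or patients are needed. The model uses four degrees of freedom more than a two-sample test, or one more than the primary model. The same change is not available for PHQ-15 or SF-36, which have no inclusion value.
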